## Using Triamcinolone Acetonide to Reduce Pain after Scleral Buckle Surgery

will be given appointments for post-operative day 1, and 1-2 weeks post-operative as is standard practice.

On post-operative day one, primary outcome data will be obtained by a blinded examiner who will be giving the patient a form which asks about the patient's pain score by reference to an 11-point numbered rating scale (0-10). On the same form, patients will also be asked about post-operative nausea and vomiting for secondary endpoint, which will be scored from 0-6 by adding the points for question II and question III from the pain and nausea survey. The form will be collected by the same examiner when completed. Pill count sheet will be collected and additional sheet will be given for patient to track analgesic use between first and second visit.

Patient will then have regularly scheduled visit with the surgeon who will be screening the patient for success of surgery, adverse events, and will examine pain and nausea scores to ensure both are well controlled. The physician will be ensuring the patient's safety, and will be allowed to prescribe any medications deemed medically necessary for control of side effects, nausea, and pain. IOP of all patients will also be measured at this visit.

At second post-operative visit (1-2 weeks), patients' IOP will be measured again for safety endpoint. Patient pill count sheet will be collected.

Patients will be filling out 11-point NRS pain score and post-operative nausea and vomiting sheet again during office visit and it will be collected by blinded examiner. Patient will then be examined by surgeon again for success of surgery, adverse events, and control of pain and nausea.

	Before Surgery	Day of Surgery	Between Surgery and First Follow-Up Visit	First Follow-Up Visit (1 day after surgery)	Between 1 st and 2 nd Follow-Up Visits	Second Follow-Up Visit (1-2 weeks after surgery)	Long-Term Follow-Up (6 months )
Location	Clinic	Surgery Center	Home	Clinic	Home	Clinic	Phone
Procedures	The doctor will explain the study to patient	Everyone: Scleral Buckle Surgery. Experimental Group: Triamcinolone (steroid) will be applied during surgery. Control Group: Saline solution will		Everyone : will be examined by the doctor for safety		Everyone : will be examined by the doctor for safety	

## Using Triamcinolone Acetonide to Reduce Pain after Scleral Buckle Surgery

		be applied during surgery.					
What Patient will do	Review and sign the consent document	Receive pill count form	Keep track of pain medication s taken on pill-count form	Fill out pain and nausea form. Turn in pill-count and receive second pill-count	Keep track of pain medication s taken on pill-count form	Fill out pain and nausea form. Turn in pill-count	Report pain level from 0-10

### 8.2 *Describe:*

- *Procedures or safeguards intended to reduce the probability and magnitude of risks.*

Patients will be screened twice for IOP (measured by tonometer) post-surgically to check for ocular hypertension. Patients eyes will also be examined at both visits by the primary surgeon via slit-lamp to determine any adverse events as a result of surgery or the intervention. The surgeon is responsible for the medical safety of all patients and may prescribe any medications deemed necessary for control of side effects of surgery or intervention, including nausea and vomiting.

- *Be sure to describe all drugs and devices used in the research, when they will be administered or used, and their purpose.*  
See 7.1

*Methods used to collect data about subjects. Please upload all data collection forms to Protocol Management*

- Pain and Nausea Survey
- Pill-Count
- IOP (tonometry)

### 8.3 *What data will you collect during the study and how you will obtain them? Please include descriptions of electronic data collection, database matching, and app-based data collection.*

Patients will be assigned an arbitrary patient ID at beginning of the study which is recorded in the EMR. Demographic data about patient age, gender, and ethnicity will be extracted from the electronic medical record. No patient identifying data including name, addresses, date of birth, or

SSN will be extracted from the electronic medical record for the purpose of the analysis. Details of surgery will be extracted from the EMR.

During the study, IOP will be collected at two time-points via tonometer. This data will be extracted from the electronic medical record for analysis. Pain level via 11-pt NRS will be collected at two time points by survey. Data about analgesic consumption will be collected via survey form at two time points by survey. Nausea and vomiting score will be collected at two time points by survey. This data will be matched to de-identified patient ID. Physical survey forms will then be confidentially discarded.

*8.4 Who will transcribe or code audio and/or video recordings?*

N/A

*8.5 Include a description of any deception to be used in the study.*

N/A

*8.6 If the study involves long-term follow-up (once all research related procedures are complete), describe what data will be collected during the follow up period and when it will occur.*

N/A

## **9.0 Data and Specimen Long Term Storage and Use**

*9.1 If you will store data or specimens for future use, describe where you will store the data or specimens, how long they will be stored, and how and by whom the data or specimens will be accessed.*

Data from the study including IOP, procedure performed, and whether or not triamcinolone was applied will continue to remain as part of patient data within Vistar Electronic Medical Record for the purposes of medical care.

*9.2 For specimens, list the data to be stored or associated with each specimen.*

N/A

*9.3 Describe the procedures to release data or specimens outside of the research team, including the process to request a release, approvals required for release, who can obtain data or specimens, and what data will be provided with specimens.*

N/A

*9.4 Describe the identifiers to be included with stored data or specimens, as well as any key or code that could be used to make them identifiable. Describe where the code will be stored, who will have access to it, and when it will be destroyed.*

Data will be stored with arbitrary patient ID and will not be identifiable. A code to re-identify patients will be with the PI ([name]) and nobody else

will have access to it. It will be destroyed after publications of the results of the study

9.5 *Please select the identifiers you will obtain (whether directly from participants or from another source), including but not limited to:*

	Name
	Geographical subdivisions smaller than a state, including street address, city, county, precinct, zip code, and equivalent geocodes (note, the initial three digits of a zip code are not considered identifiable)
	Elements of dates (except year) for dates directly related to an individual, including birth date, admission date, discharge date, date of death, and single year of age over 89 and all elements of dates (including year) indicative of such age (note, such ages and elements may be aggregated into a single category of age 90+)
	Phone numbers
	Fax numbers
	Electronic mail addresses (e-mail)
	Social Security numbers
	Medical record numbers
	Health plan beneficiary numbers
	Account numbers
	Certificate/license numbers
	Vehicle identifiers and serial numbers, including license plate numbers
	Device identifiers and serial numbers
	Web Universal Resource Locators (URLs)
	Internet protocol (IP) address numbers
	Biometric identifiers, including finger and voice prints (audio recording)
	Full face photographic images and any comparable images (including video recording)
	Student record number or identification number
	User name for online or computer accounts
	Any other unique identifying number, characteristic, or code (note this does not mean the unique code assigned by the investigator to code the data): (Explain)

## 10.0 Sharing of Results with Subjects

10.1 *Describe whether you will share results (study results or individual subject results, such as results of investigational diagnostic tests, genetic tests, or incidental findings) with subjects or others (e.g., the subject's primary care physician). If so, describe how you will share the results and*

*include this information as part of the consent document. Upload materials you will use to explain the results to subjects.*

We will not be sharing results with subjects.

## 11.0 Study Timelines

### 11.1 Describe:

- *The duration of an individual subject's participation in the study (for example, 1 hour, 2-4 weeks, 3-5 years).*
- **6 months**
- *The amount of time expected to enroll all study subjects (weeks, months, years, etc.)*
- **Approximately 17-24 months**
- *The amount of time expected for the investigators to complete this study including primary data analyses.*
- **Approximately 2.5 years**

## 12.0 Inclusion and Exclusion Criteria

### 12.1 Describe how you will screen individuals for eligibility. When will screening occur and what procedures will you use? Upload any screening scripts or surveys to Protocol Management.

Individuals will be screened at time of diagnosis. All patients who are determined to need scleral buckle surgery for rhegmatogenous retinal detachment will be screened for eligibility. Screening for the trial will be done by the surgeon, who will be reviewing the medical history at time of visit via EMR. If patient does not fail the exclusion criteria, the patient will be consented for enrollment in the trial. There are no screening scripts or surveys that will be used.

### 12.2 Describe the eligibility criteria that define who will be included and who will be excluded from enrollment for each procedure of your study.

Inclusion Criteria: Patient must have rhegmatogenous retinal detachment and be scheduled to undergo scleral buckle surgery for correction.

Exclusion Criteria:

- Patient under 18 years old
- Advanced Glaucoma
- History of corticosteroid responsive elevation in IOP
- Allergy to Triamcinolone Acetonide or other corticosteroids
- Pre-existing chronic pain disorders
- Herpes zoster
- Prior corneal allograft
- Allergy to local anesthetic or penicillin

- Patients unable to consent on own behalf
- Patients unable to communicate pain and nausea levels
- Pregnancy
- Incarceration

*12.3 Indicate specifically whether you will include or exclude each of the following special populations: (You may not include members of these populations as subjects in your research unless you indicate them in the description of your subject population.)*

All of the following populations will be excluded from our study.

- *Minors, as defined by state law where the study is performed (infants, children, teenagers)*
- *Pregnant women*
- *Prisoners (including all incarcerated individuals)*
- *Adults not capable to consent on their own behalf*

## 13.0 Vulnerable Populations

*13.1 If the research involves individuals who are vulnerable to coercion or undue influence, please describe additional safeguards you will include to protect their rights and welfare.*

N/A

## 14.0 Number of Subjects

*14.1 Indicate the total number of subjects to be enrolled and how this number was determined*

Sample Size Calculation as performed by [name] of VT and VTCSOM

$H_0$  = median post-operative pain equal in experimental and control groups

$H_A$  = median post-operative pain not equal in experimental and control groups

Median Pain Score Experimental: 1. SD = 1, IQR = 0-2

Median Pain Score Control: 3. SD = 2.5, IQR = .5 – 5.5

Alpha = .01, Power = 0.8

Effect Size,  $d$  = 1.05

Sample Size:  $n$  = 48

*14.2 If this is a multi-site study, indicate the number of subjects to be enrolled at this site and the total to be enrolled from all sites.*

n/a

14.3 *If applicable, indicate the number of potential subjects you expect to screen for enrollment, and the number of subjects you will need to complete the research procedures.*

n/a

14.4 *If the study has more than one procedure, indicate the total number of subjects to undergo each procedure separately.*

n/a

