## 4.0 Study Endpoints

### 4.1 *Describe the primary and secondary study endpoints*

Primary Endpoint:

- Statistically significant reduction in pain as measured by 11-point Numerical Rating Scale at 1-day post-op. We are powered to detect a reduction in 2 points on the NRS scale.

Secondary Endpoints:

- Statistically significant reduction in pain as measured by 11-point Numerical Rating Scale at 1-2 weeks post-op.
- Statistically significant reduction in pain as measured by 11-point Verbal Rating Scale at 6 months post-op.
- Significant reduction in analgesics consumed post-operatively (self-reported pill count) at 1-day post op
- Significant reduction in analgesics consumed post-operatively (self-reported pill count) at 1-2 weeks post op
- Significant reduction in Nausea and Vomiting Score at 1 day post-op.
- Significant reduction in Nausea and Vomiting Score at 1-2 weeks post-op.

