## 5.0 Study Design and Statistical Analysis Plan

*5.1 Describe the basic study design/approach*

Simple randomized controlled trial comparing two groups in reducing post-operative pain from scleral buckle surgery -

1. Peribulbar irrigation of triamcinolone acetonide (Experimental Group)
2. Balanced Salt Solution (Control Group)

*5.2 Describe corresponding data analysis plan/approach*

Parametric analysis of experimental and control groups using students' t-test for primary endpoint, secondary endpoint of pain and analgesic consumption will be analyzed similarly. Secondary endpoints of nausea and vomiting score will be analyzed via non-parametric analysis (Mann-Whitney U test)

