## **18.0 Potential Benefits to Subjects**

*18.1 Describe the potential benefits that individual subjects might experience from participating in the research. Include the probability, magnitude, and duration of the potential benefits, as this will be useful to the IRB's risk:benefit analysis. Do not include benefits to society or others. These should be included in section 2 or 3 of this document.*

The largest benefit to subjects is the possibility to directly reduce pain following scleral buckle surgery. This is our primary outcome so the exact likelihood and magnitude are currently unknown, but likelihood is presumed to be high based on background literature. Magnitude is presumed to be around 50% reduction in pain. Subjects may also experience a decrease in intraocular inflammation, and post-operative nausea and vomiting. Furthermore, patients may have a reduced risk for addiction to pain medication, as we hope to demonstrate a reduced need for post-operative analgesics following surgery. All patients in the experimental group will also be receiving the treatment at no additional cost to them, which is a potential financial benefit.

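### Do the interquartile ranges in 14.1, each exactly median ± 1 SD, undermine the effect size and the sample size of 48?

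*Combined protocol and SAP*

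**What the plan says.** Section 14.1 sets out the sample size. The experimental arm is entered as "Median Pain Score Experimental: 1. SD = 1, IQR = 0-2" and the control arm as "Median Pain Score Control: 3. SD = 2.5, IQR = .5 – 5.5". The error rates are "Alpha = .01, Power = 0.8". The alternative hypothesis is "median post-operative pain not equal in experimental and control groups", so the test is two-sided. The section then gives d = 1.05 and n = 48. It cites no source for the medians, SDs or ranges.

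Section 4.1 says of the primary endpoint: "We are powered to detect a reduction in 2 points on the NRS scale". Section 5.2 plans the comparison as "Parametric analysis of experimental and control groups using students' t-test for primary endpoint". Section 8.1 describes the pain score as an 11-point scale from 0 to 10.

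**The concern.** Two ranges that both land exactly on median ± 1 SD are unlikely to be a coincidence. For normal scores, the model behind Cohen's d and the t-test, the quartiles lie 0.6745 SD either side of the centre, not a full SD. So the stated spread appears in two forms that do not agree under the planned model.

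There are two natural explanations. The ranges may be ± 1 SD intervals labelled as IQRs, in which case only the label is wrong. Or they may be real quartiles, with each SD taken as half the width, in which case the SDs may be too small. Under the second, d would be too large, the power for 2 points would be below the stated 80%, and a null result from 48 patients could be read as stronger evidence against a 2-point benefit than it is.

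**Working it through.** **Inputs.** From 14.1: medians 1 and 3, SDs 1 and 2.5, alpha .01, power 0.80, two-sided. From 8.1: coin-flip allocation, taken here as 24 per arm. From 5.2: Student's t-test.

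**Reproducing the plan's figures**

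- Pooled SD = √((1² + 2.5²)/2) = √3.625 = 1.904.
- d = (3 − 1)/1.904 = 1.0505, which is the stated 1.05.
- Noncentral t with 24 per arm: df = 46, noncentrality = 1.0505 × √(24/2) = 3.64, critical value 2.687, power 0.824. With 23 per arm power is 0.803, so the t-test alone needs 46.
- Multiplying the per-arm n by the Mann-Whitney efficiency 3/π gives power 0.801 at 24 per arm and 0.778 at 23, so 48 in total.

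The stated n is therefore right for the stated SDs. The printed ranges are used nowhere in this chain.

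**The coincidence**

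- Experimental: 1 − 1 = 0 and 1 + 1 = 2. Control: 3 − 2.5 = 0.5 and 3 + 2.5 = 5.5. Both match the printed ranges.
- Normal quartiles from the printed SDs: 1 ± 0.6745 × 1 = 0.33 to 1.67; 3 ± 0.6745 × 2.5 = 1.31 to 4.69. Neither matches.

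**Can all the printed values be true together?** The scale is bounded and takes whole numbers, so the normal ratio of IQR to SD need not apply. A constructed example (not trial data):

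| Arm | Probabilities for scores 0, 1, 2, … | Mean | SD | Median | Quartiles |
|---|---|---|---|---|---|
| Experimental | .37 .33 .24 .04 .02 | 1.01 | 0.97 | 1 | 0, 2 |
| Control | .25 .10 .12 .12 .08 .08 .18 .05 .02 | 3.01 | 2.47 | 3 | 0.5, 5.5 |

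The control quartiles use the midpoint convention: the cumulative probability is exactly .25 at 0 and .75 at 5. The mean difference is 2.00. In 40,000 simulated trials with 24 per arm, t-test power at .01 is 0.85. The printed medians, ranges and SDs (to within rounding) can therefore coexist with the claimed power.

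**What larger SDs would do** (2-point difference, 24 per arm, two-sided .01)

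| SDs | Basis | Power |
|---|---|---|
| 1 / 2.5 | as printed | 0.82 |
| 1.1 / 2.75 | both 10% larger | 0.73 |
| 1.2 / 3.0 | both 20% larger | 0.64 |
| 1.53 / 3.12 | a second constructed 0–10 pair with the same medians and quartiles | about 0.57 |
| 1.48 / 3.71 | unbounded normal, SD = range width/1.349 | 0.42 |

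The last row is an outer bound only, because it puts 25% and 21% of scores below zero. Every row after the first replaces the SDs that 14.1 prints. These rows show how power depends on the SD; they do not follow from the text of the plan.

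**The case for a change.** The strongest case for a change is that quartiles alone do not fix the SD on this scale. Two distributions with identical medians and quartiles, and mean differences of about 2, give power of 0.85 and about 0.57. There is also little slack: 80% power needs d = 1.0237, so the largest tolerable pooled SD is 2/1.0237 = 1.954, only 2.6% above 1.904. With no source cited, a reader cannot rule out understated SDs.

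That much is true, and only the sponsor can say where the SDs came from. But the thin margin comes from solving for 80% and would appear in any trial sized that way; it is not evidence that these SDs are wrong. The second distribution reaches its lower power by having SDs of 1.53 and 3.12, which are not the planned values.

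Section 4.1 carries no SD condition, but every power statement rests on its planning inputs, and those are set out in 14.1. The risk of over-reading a null result is limited too: what such a result excludes depends on the confidence interval from the observed SDs, not on the planning SDs.

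Section 18.1 adds "Magnitude is presumed to be around 50% reduction in pain", while the planning medians imply (3 − 1)/3 = 67%. That statement gives no baseline. Applying it to a control value of 3 (1.5 points, power 0.52) would be an assumption brought from outside the plan.

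**Conclusion.** No change to the plan is called for. The observation is correct: both ranges equal median ± 1 SD exactly, and the documents do not say whether they are quartiles or ± 1 SD intervals. But no figure the trial relies on is shown to be wrong. d = 1.05, n = 48 and 80% power follow from the printed SDs (t-test power 0.82; 0.80 with the Mann-Whitney allowance), and the ranges play no part in them.

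If the ranges are mislabelled ± 1 SD intervals, this is a clerical slip with no effect on size or power. If they are quartiles, SDs of 1 and 2.5 are still attainable on a 0 to 10 scale. Only a source showing different SDs would alter the power, and none appears in the documents. Naming the source and the type of range would make 14.1 easier to read, but would not by itself change enrolment, conduct or analysis.

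This conclusion assumes 24 per arm, a two-sided alpha of .01 and a 2-point difference in means, with the planning medians standing in for means as the plan's own d does.

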## 16.0 Withdrawal of Subjects

16.1 *Describe circumstances under which you anticipate subjects could be withdrawn from the research without their consent.*

- The research is canceled by the FDA or the sponsor
- Patient is unable to keep scheduled appointments
- A patient has a side effect that requires stopping the research

*16.2 If applicable, describe any procedures for orderly termination (e.g., discontinuation of a study drug or debriefing after a behavioral intervention).*

N/A

*16.3 Describe procedures that you will follow when subjects withdraw from the research, including partial withdrawal from procedures with continued data collection (e.g., participant declines to continue with regular blood draws, but continues with periodic behavioral questionnaires).*

If the patient withdraws consent to study before the time of surgery, the patient will not receive either the experimental or control treatments, and will receive standard surgical treatment. The patient's data will not be extracted from the EMR for study purposes, and the patient will not be given any of the survey materials. If a patient withdraws consent after the surgery, the patient's data will not be extracted from the EMR for analysis and the patient will be given no further survey materials. Existing survey materials will be destroyed. If patient partially withdraws from procedures after surgery, the data may be used except for that which is not completed.

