## 8.0 Procedures Involved

8.1 *Describe and explain the study design.*

Randomized Control Trial. Subjects will be patients at Vistar Eye Center who are undergoing scleral buckle surgery for rhegmatogenous retinal detachment. Patients of this indication will be consented and enrolled in the trial as detailed in section 24, and randomized (by coin-flip) into one of two arms, the control or the experimental. Patients in both arms of the study will be screened for IOP via handheld digital tonometry (tonopen) and will undergo standard scleral buckle procedures, including irrigation with 1 ml .75% Marcaine for local anesthesia (as is standard for all surgeries). At time of surgery, patients in the experimental group will receive irrigation of 1 ml (40 mg/mL) triamcinolone around the bed of applied scleral buckle distributed equally in all 4 quadrants (.25 ml per quadrant) under the tenon layer of the eye. Patients in the control group will be given irrigation around the applied scleral buckle of 1 ml balanced salt solution instead of triamcinolone. Patients will be masked to the treatment group assignment. The surgeon cannot be masked, as the triamcinolone solution is white and the balanced salt solution is clear. Intraoperative details will be recorded in the EMR about the surgery in both groups, including duration of surgery, time of irrigation, any additional pharmaceuticals or anesthesia applied, procedures performed, and placement of the buckle. Patient will receive a pill-count form at the end of the visit to keep track of rescue analgesic consumption. All patients

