## Using Triamcinolone Acetonide to Reduce Pain after Scleral Buckle Surgery

The patient will be consented in the clinic patient exam room, immediately following consultation with the doctor about the planned surgical procedure. The consultation will be done by the doctor who is well trained on the procedures and risks. The doctor will also be able to answer any more specific questions that the patient may have.

- *The time interval between sharing the consent information with the prospective subject and obtaining consent. For lab, interview, and focus group studies, the Virginia Tech IRB prefers that subjects have at least 24 hours to review the consent form and study information before the appointment where consent will be obtained. For simple online survey studies, you can typically present the consent information immediately before subjects begin participation.*

The obtaining of consent will occur directly after the sharing of consent information. However, the patient will be given a copy of the consent forms and the surgery will not usually take place until the next day or longer still, giving the patient sufficient time to review the materials and change their decision to withdraw or provide consent by notifying any staff member up until the moment right before surgery.

- *If applicable, processes to ensure ongoing consent or assent (e.g., for multiple sessions; for research in which a minor will turn 18 during the study; for longitudinal research with minors who will later be asked to provide or affirm their assent).*

As there is no more than minimal risk to the patient after the original intervention, we do not believe this is necessary.

- *Please review “SOP: Informed Consent Process for Research (HRP-090)” for recommended procedure. Describe your process, being sure to include:*
  - *The name and role of all study personnel who will be trained and certified by the PI to conduct the consent process*
    - [name] M.D. (PI)
    - [name] Jr. M.D.
    - [name], Medical Student, Research Coordinator
  - *The time that will be devoted to the consent discussion*  

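### Section 16.1 permits withdrawal from the research for a side effect or for inability to attend after a one-time treatment, so patients with early side effects may be missing from the 1-2 week safety comparison and later follow-up

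*Combined protocol and SAP*

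**What the plan says.** Section 16.1 answers a template question about "circumstances under which you anticipate subjects could be withdrawn from the research without their consent". Besides cancellation of the research, it gives two grounds: "Patient is unable to keep scheduled appointments" and "A patient has a side effect that requires stopping the research". It gives no criterion for which side effects qualify, no number of missed visits, and no statement of who decides.

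Section 8.1 fixes the intervention to one occasion: "At time of surgery, patients in the experimental group will receive irrigation of 1 ml (40 mg/mL) triamcinolone". Section 16.2, on orderly termination, is marked not applicable. After surgery, 8.1 and its schedule table leave only pain and nausea forms, pill counts, IOP readings at two routine visits, the surgeon's examinations, and a 6-month phone call at which the patient is to "Report pain level from 0-10". Section 24.1 declines an ongoing consent process with the words "As there is no more than minimal risk to the patient after the original intervention".

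Section 16.3 covers two situations after surgery. For withdrawn consent: "If a patient withdraws consent after the surgery, the patient's data will not be extracted from the EMR for analysis", and survey forms already completed are destroyed. For partial withdrawal: "If patient partially withdraws from procedures after surgery, the data may be used except for that which is not completed". Withdrawal by the team is not covered.

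**The concern.** A side-effect ground for withdrawal makes sense when dosing continues and can be stopped. Here nothing of the study treatment remains after the irrigation, so removing a patient from the research ends only observation.

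The reason for removal can be the outcome itself. The safety endpoints in 4.2 are ocular hypertension at 1-2 weeks (IOP more than 5 mmHg above baseline), infection and hypersensitivity. IOP is also read on day 1, and the surgeon looks for adverse events then. A patient could therefore be withdrawn after day 1 because of an event that bears directly on the 1-2 week reading, and that reading would then be absent.

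Loss of this kind depends on outcome. If triamcinolone raises IOP, more patients are exposed to it in that arm. Because 4.2 frames each safety endpoint as the absence of a significant difference, lost cases push toward the conclusion the plan hopes for. The 1-2 week pain, nausea and pill-count data and the 6-month pain score go missing for the same patients. The safety review in 21.1 is triggered by every tenth patient to complete the protocol, and the text does not say whether withdrawn patients enter it.

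The attendance ground has a related problem. The 6-month endpoint is collected by phone, so inability to attend clinic is no reason to lose it.

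**Working it through.** **Plan figure.** Section 16 contains no figure to reproduce. The only plan figure used is N = 48 (14.1). Its stated inputs give d = 2/√((1² + 2.5²)/2) = 2/1.904 = 1.05, as stated. A two-sided t-test at alpha 0.01 and 80% power needs 23 per arm, or 46, so 48 is close. An equal split gives 24 per arm. This is an assumption, since allocation is by coin flip.

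**What withdrawal can stop, by time.**

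| Time | Study activity remaining | What withdrawal would stop |
|---|---|---|
| Before irrigation | Irrigation and all follow-up | Study treatment and data |
| After irrigation, before day-1 form | All follow-up data | Data only, including the primary score |
| After day-1 form | 1-2 week IOP, forms, pill count; 6-month call | Data only; primary score already collected |

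On day 1 the masked examiner collects the pain form before the surgeon's examination (8.1). A side effect found at that examination therefore comes after the primary outcome is recorded.

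**Illustration 1: equal share of cases withdrawn in both arms.** Assumptions: 24 per arm; control rate of IOP rise 10%; two-sided alpha 0.05 (the plan states none for safety); triamcinolone rate p of 20%, 40% or 60%, the range that 17.1 cites for injection. A fraction f of would-be cases is withdrawn before the 1-2 week reading.

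Observed rate = p(1 − f)/(1 − pf). Power ≈ Φ[(difference − 1.96·SE₀)/SE₁], with SE₀ from the pooled rate and SE₁ from the separate rates.

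Worked case, p = 40%, f = 0.5:
- Triamcinolone: 0.20/0.80 = 25% of 19.2 patients. Control: 0.05/0.95 = 5.3% of 22.8.
- Difference: 19.7 points, against 30 with no withdrawals.
- Power: SE₀ = 0.108, SE₁ = 0.109, giving 45%. With no withdrawals SE₀ = 0.125, SE₁ = 0.117, giving 68%.

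| True triamcinolone rate | Difference, f = 0 | Difference, f = 0.5 | Power, f = 0 | Power, f = 0.25 | Power, f = 0.5 |
|---|---|---|---|---|---|
| 20% | 10 points | 6 points | 16% | 13% | 11% |
| 40% | 30 points | 20 points | 68% | 58% | 45% |
| 60% | 50 points | 38 points | 98% | 93% | 82% |

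With f = 1 the observed difference is zero at any rate. The normal approximation is rough at these counts.

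**Illustration 2: withdrawals in one arm.** Assume 8/24 (33.3%) against 4/24 (16.7%), a difference of 16.7 points. If three affected triamcinolone patients are withdrawn, the data show 5/21 (23.8%) against 4/24 (16.7%), or 7.1 points. Fisher's exact p is 0.32 before and 0.71 after. The estimate shrinks by more than half, but the test is non-significant either way.

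**The case against.** The strongest reply is that the rule would seldom operate. It is permissive, and it applies only where a side effect requires the research to stop. If nothing remains to stop after surgery, few post-operative events should meet that condition. The line also has a proper use before irrigation. Elsewhere the protocol expects side effects to be treated and watched: the surgeon may prescribe for them (8.1, 8.2), routine visits continue, IOP stays in the medical record (9.1), and possibly related events go promptly to the IRB (21.1). This stands as a limit on the point. It does not close it, because an IRB report is not a comparison between arms, and no section available to me (6.0 was not) keeps a withdrawn patient in follow-up or analysis.

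A reader might infer more than the documents support:

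- **That affected patients do leave follow-up.** The text says only that they could be withdrawn.
- **That one withdrawal can erase an infection or hypersensitivity signal.** An event that prompts withdrawal has already been observed, and nothing in 16.3 deletes data collected before a team withdrawal. The destruction rule is written for withdrawn consent.
- **That one missed visit is enough.** Being unable to keep appointments is narrower.
- **That the unmasked surgeon decides.** Section 16.1 does not say who does.
- **That the primary result is compromised.** The day-1 form precedes the surgeon's examination.

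**Conclusion.** The point holds in limited form. Section 16.1 allows removal from data collection for reasons tied to the safety outcomes, at a stage when removal protects no one from further study treatment, and 16.3 leaves the status of the data open. What is exposed is the 1-2 week IOP comparison, the other 1-2 week data, the 6-month call and possibly the periodic safety review. The likely direction is toward no difference in safety. The day-1 primary pain score is largely unaffected, apart from a patient withdrawn before completing that form.

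The documents do not give the size of the bias. The figures above rest on assumed event rates and assumed shares withdrawn, and section 17.1 expects a rate well below the cited 20-60%. At the low end the safety comparison has little power even with no withdrawals (16% at 20% against 10%), so the main harm there is a distorted estimate rather than a changed test result. The change is worth making because it is cheap and uncollected readings cannot be recovered.

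**What to change.** In 16.1:
- Limit the side-effect ground to events before the irrigation.
- State that every treated patient stays in the planned IOP, adverse-event, pain and 6-month data collection, and is analysed as randomised, unless consent is withdrawn.
- Replace the attendance ground with a statement that a patient who cannot attend has that visit's data recorded as missing and is still called at 6 months.

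In 16.3, state that data from any subject withdrawn by the team are retained and used.

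These changes concern data collection only, and clinical care stays with the surgeon. The cost is a few lines of protocol and matching consent wording. No visits are added, because the two clinic visits are routine care and the call is already planned.
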